5.2.8. Safety Laboratory

Observed and changes from baseline in laboratory values will be summarized by treatment group and scheduled visit. Safety laboratory parameters to be summarized include complete blood count (hemoglobin, platelets, leukocytes), differential (absolute counts of basophils, eosinophils, lymphocytes, monocytes, total neutrophils), renal/liver (BUN, creatinine, alanine

aminotransferase, aspartate aminotransferase, total bilirubin, direct bilirubin, total protein), and coagulation (aPTT, INR).

Laboratory abnormalities considered clinically significant will be entered by the investigators as adverse events and graded, classified by causality and included in the AE listings and tables accordingly.

By-subject listings will be provided for laboratory parameters of blood chemistry, hematology, and coagulation studies. Laboratory values outside the corresponding normal ranges will be flagged in listings.

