- SARS-CoV-2 diagnostic test result
 - Diagnostic testing must be an approved molecular or antigen diagnostic test for SARS-CoV-2 from any upper respiratory specimen performed at screening or enrollment or within 5 days of enrollment. The test used must be authorized for use by the relevant national authority for the detection of SARS-CoV-2 in the country where the test is administered. Historical testing results will be acceptable if testing performed within the required window. The test result must be available and reviewed by site PI or study staff to confirm eligibility.

C 9.2.5 Blood Volumes

The maximum volume of blood drawn at any one visit will not exceed 30 mL.

C 9.2.6 Pharmacokinetics

Plasma samples for PK evaluation will be collected at Day 0, Day 3, and Day 14. The analysis will include levels of upamostat and its active metabolite, WXUK1, for each of these time points.

Day 0: all patients will have a specimen drawn prior to first treatment with study medication.

Patients will be randomized to one of two sampling regimens for Day 3:

A) Day 3 specimen within 2 hours prior to dosing;

OR

B) Day 3 specimen 2-4 hours after dosing.

Day 14: all patients will have a specimen drawn 22-26 hours after previous dose.

An attempt will be made to get a specimen 22-26 hours after the last dose from patients who stop treatment early.

C 9.4 Study Visits

Study Visits will be conducted according to the Master Protocol with the following additions and exceptions as presented in [Section 1.2 Schedule of Activities](#).

Activities in the Master Protocol that do not apply to participants randomized to the upamostat Appendix C are indicated by ~~strikethrough~~, while activities that have been added are indicated by **bold** text.

C 9.4.1 Screening Visit – In Person or Remote (Within 24 hours Prior to Enrollment)

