- Screening Symptom Questionnaire (repeat if visit not performed on same day as Screening)
- Randomization (Step 1)
- Study (IP) Informed Consent (in person)
- Screening assessments (see [Section C 9.2.3 Screening Assessments](#))
- **ECG**
- Eligibility evaluation (review of all screening and eligibility assessments)
- Randomization (Step 2)
- Upper respiratory specimen collection (prior to administration of upamostat or control) (for efficacy assessment)
- Venous blood sampling (prior to administration of upamostat or control)
 - Hematology (prior to administration of upamostat or control)
 - Chemistry (prior to administration of upamostat or control)
 - **Coagulation Studies**
 - **Anti-SARS-CoV-2 IgM and IgG**
 - **Polymorphisms of relevant host cellular proteases**
 - **Whole Blood, Plasma and Serum Storage for Possible Future Research (prior to administration of upamostat or control)**
 - **Pharmacokinetics**
- **Administration of upamostat or control**
- Collect and update contacts
- Dispense study kit
- Adverse event recording and reporting

C9.4.3 Day 3 Visit – ~~Remote~~ or In Person

This visit is scheduled to take place In Person on Day 3. Every effort should be made to complete the Day 3 visit requirements on Day 3; however, the visit may take place — if necessary +/- 1 days.

- ~~SARS-CoV-2 Vaccination Status~~
- Concomitant medication review
- Collect and update contacts
- Daily Symptom Follow Up Questionnaire (daily until day 28 then at **Weeks 8** and 12)
- Upper respiratory specimen collection
- Clinical outcome assessment
- Vital signs
- Physical exam
- Venous blood sampling (for Pharmacokinetics Group A: venous blood sampling should be collected within 2 hours prior to administration of upamostat or control, for Pharmacokinetics Group B: venous blood sampling should be collected 2-4 hours after administration of upamostat or control)
 - Hematology
 - Chemistry
 - **Coagulation studies**
 - **Whole blood, plasma, and serum storage for possible future research**
 - **Pharmacokinetics**
- **ECG**
- Adverse event recording and reporting

C 9.4.4 Day 7 Visit- ~~Remote~~ or In-person

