This visit is scheduled to take place Remotely on Day 7. Every effort should be made to complete the Day 7 visit requirements on Day 7; however, the visit may take place — if necessary +/- 1 days. Remote visits may include visits by the study staff to the participant or via phone/video conference. If remote visit not feasible or is not permissible under local rules or standards, the visit may be conducted in person.

- ~~SARS-CoV-2 Vaccination Status~~
- Concomitant medication review
- Collect and update contacts
- Daily Symptom Follow Up Questionnaire (daily until Day 28 then at **Weeks 8** and 12)
- Upper respiratory specimen collection (self-collection)
- Clinical Outcome Assessment
- Adverse event recording and reporting

C 9.4.5 Day 10 Visit- Remote

This visit is scheduled to take place Remotely on Day 10. Every effort should be made to complete the Day 10 visit requirements on Day 10; however, the visit may take place — if necessary +/- 1 days. Remote visits may include visits by the study staff to the participant or via phone/video conference. If remote visit not feasible or is not permissible under local rules or standards, the visit may be conducted in person.

- Daily Symptom Follow Up Questionnaire (daily until Day 28 then at **Weeks 8** and 12)
- Concomitant medication review
- Upper respiratory specimen collection (self-collection)
- Adverse event recording and reporting

C 9.4.6 Day 14 Visit – In Person

This visit is scheduled to take place In Person on Day 14. Every effort should be made to complete the Day 14 visit requirements on Day 14; however, the visit may take place — if necessary +/- 2 days

- ~~SARS-CoV-2 Vaccination Status~~
- Concomitant medication Review
- Daily Symptom Follow Up Questionnaire (daily until Day 28 then at **Weeks 8** and 12)
- Upper respiratory specimen collection
- Clinical outcome assessment
- Vital signs
- Physical exam
- Venous blood sampling (should be collected from all participants 22-26 hours after previous dose of upamostat or control)
 - Hematology
 - Chemistry
 - **Coagulation studies**
 - **Whole blood, plasma, and serum storage for possible future research**
 - **Pharmacokinetics**
- **ECG**
- Adverse Event Recording and Reporting

C 9.4.7 Day 28 Visit – In Person

This visit is scheduled to take place In Person on Day 28. Every effort should be made to complete the Day 28 visit requirements on Day 28; however, the visit may take place — if necessary +/- 4 days.

- ~~SARS-CoV-2 Vaccination Status~~

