5.2.7. Electrocardiogram

Observed and changes from baseline QTc Fridericia (QTcF) interval data will be summarized by treatment group, cohort and scheduled visit. A listing of all results will be provided.

QTcF will be calculated as

$$QTc = \frac{QT}{RR^{1/3}}$$

where QT is the QT interval duration and RR is the interval between R waves.

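### SAP 5.2.8 pools Day 3 safety bloods drawn pre-dose (PK group A) and 2-4 h post-dose (group B), so the only scheduled laboratory sample soon after a dose is not reported separately

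*SAP*

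**What the plan says.** Protocol C 9.2.6 sets two Day 3 schedules by randomisation: "Patients will be randomized to one of two sampling regimens for Day 3". They are "A) Day 3 specimen within 2 hours prior to dosing" and "B) Day 3 specimen 2-4 hours after dosing". The section gives no allocation ratio.

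Protocol C 9.4.3 applies this timing to the Day 3 venous draw as a whole ("for Pharmacokinetics Group A: venous blood sampling should be collected within 2 hours prior to administration of upamostat or control", with group B at 2-4 h after). Hematology, chemistry, coagulation, stored samples and PK are all listed beneath that draw. The ECG is a separate item, outside it.

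At Day 14 there is one schedule. Under C 9.4.6 the blood "should be collected from all participants 22-26 hours after previous dose of upamostat or control".

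SAP 5.2.8 gives the laboratory summary: "Observed and changes from baseline in laboratory values will be summarized by treatment group and scheduled visit". It adds by-subject listings with out-of-range flags, and adverse-event entry for abnormalities that the investigator judges clinically significant. PK sampling group is not used as an analysis factor anywhere in the SAP, and SAP 7 places pharmacokinetic analysis outside the plan.

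**The concern.** The trial randomises two exposure conditions at Day 3 and then tabulates them as one. This matters most for coagulation, the laboratory effect that the protocol itself flags. In the pilot COVID-19 study, INR or aPTT rose by at least one grade in 25% of placebo patients, 50% at 200 mg and 62% at 400 mg (C 3.4.1.1). INR and PTT also have their own pause criteria for individuals and for the product arm (C 12.1, C 12.2).

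If the effect on clotting times is larger in the hours after a dose than at the end of the dosing interval, a reader of the Day 3 row would see a blend of the two and could take it for the on-treatment effect. The by-visit summary is the only aggregate laboratory comparison in SAP 5.2.8. No exposure-response analysis elsewhere in the SAP would recover the contrast.

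**Working it through.** **1. Is there another scheduled post-dose laboratory sample?** Taking the visits in C 9.4 in turn:

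- Day 0: the venous draw precedes the first dose.
- Day 3, group A: within 2 h before the dose. Group B: 2-4 h after it.
- Days 7 and 10: no venous blood.
- Day 14: 22-26 h after the previous dose, for everyone.
- Day 28 and Week 8: after the 14-day course has ended.

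Group B at Day 3 is therefore the only scheduled safety blood sample within a few hours of a dose.

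**2. What does the pooled Day 3 row estimate?** The documents state no figure to reproduce. Define:

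- d: the upamostat-placebo difference at 2-4 h post-dose;
- f: the pre-dose difference as a fraction of d (not in the documents);
- w: the share of participants in group B, taken as equal in both arms (not in the documents).

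Pooled difference = w·d + (1 - w)·f·d, so pooled / d = w + (1 - w)f.

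| w | f = 0 | f = 0.25 | f = 0.5 | f = 0.75 | f = 1 |
|---|---|---|---|---|---|
| 1/3 | 33% | 50% | 67% | 83% | 100% |
| 1/2 | 50% | 62.5% | 75% | 87.5% | 100% |
| 2/3 | 67% | 75% | 83% | 92% | 100% |

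For example, at w = 0.5 and f = 0.5: 0.5 + 0.5 × 0.5 = 0.75.

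**3. Scale, as an illustration only.** Treat the pilot's 62% as if it were a 2-4 h rate and 25% as background. Both are assumptions, since the pilot rates carry no sampling time. The excess is 62 - 25 = 37 points. At w = 0.5 and f = 0 the pooled rate is (62 + 25)/2 = 43.5%, an excess of 18.5 points. At f = 0.5 the group A rate is 25 + 0.5 × 37 = 43.5%, and the pooled rate is (62 + 43.5)/2 = 52.75%, an excess of 27.75 points. C 5.4 gives the 400 mg rate as 65% rather than 62%. With that figure the f = 0 result is 20 of 40 points. The two sections should be reconciled.

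**4. Precision.** Under an equal split each cell has half the participants, so an interval widens by √2 ≈ 1.41. With equal standard deviations, the ratio of effect to standard error in group B alone, relative to pooled, is √2/(1 + f): 1.41 at f = 0, 1.13 at f = 0.25 and 0.94 at f = 0.5. They are equal at f = √2 - 1 ≈ 0.41. This ratio does not depend on the sample size.

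**The case against.** The strongest reply is that nothing here is biased. The sampling regimen is randomised with no stated dependence on arm, so the pooled upamostat-placebo contrast is a legitimate average over sampling times. SAP 5.2.8 is descriptive, mean laboratory change is not among the SAP 3.4 safety endpoints, and above f of about 0.41 the pooled contrast is the more precisely determined one. This stands. The pooled row should stay, and the point is that it answers a different question from the post-dose one.

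The second reply is that safety does not rest on this table. Listings, out-of-range flags, adverse-event entries, the individual and product-level pause rules and monthly unblinded DSMB review all use unpooled values or sit outside the summary. This also stands, so a reader should not infer that individual signals would be missed. None of these, however, estimates the difference between arms after a dose.

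Three stronger readings are tempting but unsupported:

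- **That half of the effect is lost.** One half is the result only for an equal split and no pre-dose effect after several daily doses. The documents give no allocation ratio, half-life or time to peak, so they do not show that 2-4 h is near the peak either. If f exceeded 1, the pooled figure would be larger than the 2-4 h effect.
- **That QTcF is diluted in the same way.** No section ties the ECG to the dose or to PK group, and SAP 5.2.7 says the QTcF "interval data will be summarized by treatment group, cohort and scheduled visit". *Cohort* is undefined there, but this does not show pooling of pre-dose and post-dose ECGs.
- **That a power loss can be quoted at 150 per arm.** No test is planned on these summaries. SAP Appendix A also records that enrolment ended before the interim trigger, which the protocol set at 150 participants reaching Day 28.

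**Conclusion.** The point holds for the Day 3 laboratory summaries, with coagulation the parameter of most interest. The protocol creates a randomised pre-dose versus 2-4 h comparison in every Day 3 safety blood, and the SAP does not report it. The pooled row is valid as an average but shows only w + (1 - w)f of the 2-4 h effect. At an assumed equal split this runs from 50% (f = 0) through 75% (f = 0.5) to no loss at all (f = 1). At f = 0 it runs from 33% to 67% as the group B share goes from 1/3 to 2/3. The size cannot be fixed further, because neither w nor f is in the documents.

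This is a gap in descriptive safety reporting. It does not affect the primary analysis, individual safety actions or any planned test. It is worth correcting because the change is small and the information cannot be had from another scheduled visit.

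**What to change.** In SAP 5.2.8, present Day 3 laboratory values and changes from baseline, INR and aPTT first, by treatment group and PK sampling group (A pre-dose, B 2-4 h post-dose). Give the upamostat-placebo difference with its interval in each group, and keep the pooled row beside them. Record the change in SAP Appendix A or in the CSR, as the SAP provides.

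The cost is one additional table split on a factor that the trial already randomises. The PK group assignment has to be carried into the analysis data even though PK analysis itself is outside the SAP. Cells are smaller: under an equal split each interval is about 1.4 times wider, and because enrolment stopped early the cells will be well below half of the planned 150 per arm. No new procedure or sample is needed.

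Two matters should be raised separately as clarifications: what *cohort* means in SAP 5.2.7, and that the protocol does not state the time of the Day 3 ECG relative to the dose.

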In the COVID-19 study, no increase in transaminases was seen at either upamostat dose level as compared to placebo. International Normalized Ratio (INR) or activated partial thromboplastin time (aPTT) were often mildly abnormal at baseline in patients in the COVID-19 study. On-study, 25% of placebo patients, 50% of upamostat 200 mg recipients and 62% of upamostat 400 mg recipients developed increases in either INR or aPTT of at least one grade per National Cancer Institute (NCI) Common Terminology Criteria for Adverse Events (CTCAE) v 5.0. Almost all increases were Grade 1; no clinical bleeding was noted.

C.3.4.1.2 Steps Taken to Minimize Risks

1. Risk to participants in this trial may be minimized by compliance with the eligibility criteria and study procedures, close clinical monitoring, as well as periodic review of all safety data by an independent data monitoring committee
2. Because upamostat may inhibit CYP3A4, patients receiving anticoagulants metabolized by CYP3A4 (warfarin, apixaban [Eliquis], or rivaroxaban [Xarelto]) may not be entered into the study, nor may these medications be started while a patient is receiving upamostat.

C 3.4.3 Assessment of Potential Risks and Benefits

This study involves potential risks to and potential health benefits for the participant. Potential benefits, along with anticipated vital knowledge the trial is likely to generate, suggest that benefits of the study outweigh the risks.

C 4 OBJECTIVES AND ENDPOINTS

C 4.1 Early Treatment

In addition to those listed in the MP, the following objectives and endpoints will be included:

	Objectives	Endpoints

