3.4. Safety Objectives

To evaluate the safety and tolerability of upamostat compared to control

- **Endpoints**
 - a) Incidence of Serious Adverse Events (SAE)
 - b) Comparison between active and placebo treatment groups in proportion of all and Grade 3 or greater adverse events (as assessed by the National Institutes of Health, Division of AIDS Table for Grading Severity of Adult and Pediatric Adverse Events [DAIDS AE Grading Table], corrected Version 2.1, July 2017)
 - c) Incidence of Adverse Events (AE) causing IP discontinuation
 - d) Incidence of all-cause IP discontinuation or interruption
 - e) Number of participants hospitalized due to adverse events regardless of cause

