- Grade 4 (Life-threatening) – Potentially life-threatening symptoms causing inability to perform basic self-care functions with intervention indicated to prevent permanent impairment, persistent disability
- Grade 5 (Death)

Safety analyses will include

- Incidence of Serious Adverse Events
- Adverse Events
- Adverse Events \geq Grade 3
- IP discontinuation due to AE
- All-cause IP discontinuation
- Hospitalization due to any adverse events

The number and percentage of participants with AEs will be summarized for each treatment group. Overall treatment group differences may be compared using Chi-square tests or Fisher's exact tests.

Serious AE and hypersensitivity reactions will also be summarized. The counts and proportion of participants experiencing these events will be reported for each treatment arm. Treatment groups may be compared by Chi-square tests or Fisher's exact tests.

Permanent discontinuations or interruptions of upamostat due to AEs will be listed. The count and proportion of discontinuations of the study drug due to AEs will be reported.

Categorical safety measures (e.g. hospitalization) will be summarized with counts and proportions of participants and may be compared by treatment using either a Chi-square test or a Fisher's exact test.

All AE will be summarized by worst DAIDS grade and presented by System Organ Class (SOC), Preferred Term (PT), and treatment group, as follows.

- All AE
- All Related AE
- All AE leading to study drug discontinuation
- All SAE

All AE data will be provided in listings. A listing of any on-study deaths will be presented.

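### The SAP keeps the endpoint of IP discontinuation or interruption but does not count interruptions by arm, and it does not tabulate INR/aPTT and liver results by grade increase, the scale the protocol uses

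*SAP*

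**What the plan says.** **Interruption.** SAP 3.4(d) lists the safety endpoint "Incidence of all-cause IP discontinuation or interruption". The protocol has the same item among its endpoints (C 4.1) and in its list of safety analyses (C 13.5.1.3). The SAP 5.2.6 list of safety analyses has "All-cause IP discontinuation" instead. Later text in 5.2.6 lists discontinuations and interruptions due to AEs, but gives a count and proportion only for discontinuations due to AEs. Neither SAP section 2 nor SAP Appendix A records a change to this endpoint.

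**Laboratory values.** SAP 5.2.8 states "Observed and changes from baseline in laboratory values will be summarized by treatment group and scheduled visit". The parameters include ALT, AST, bilirubin "and coagulation (aPTT, INR"). Two other displays are planned:

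- "Laboratory abnormalities considered clinically significant will be entered by the investigators as adverse events and graded". These then enter the 5.2.6 tables, where "All AE will be summarized by worst DAIDS grade and presented by System Organ Class (SOC), Preferred Term (PT), and treatment group".
- "Laboratory values outside the corresponding normal ranges will be flagged in listings".

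**The protocol's scale.** Protocol C 3.4.1.1 describes the pilot coagulation finding by grade: 25% on placebo, 50% at 200 mg, and "62% of upamostat 400 mg recipients developed increases in either INR or aPTT of at least one grade" under CTCAE v5.0. C 12.1 writes the individual pause rules for INR/PTT (more than 2 grades over baseline) and for transaminases and bilirubin (more than 1 grade) on the DAIDS scale. The laboratory criteria for a study-level pause (C 12.2, Table 1) also use grade increases.

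**The concern.** A declared safety endpoint lacks part of its planned summary. Under C 12.1 the INR/PTT and liver rules first pause the drug, and the participant may resume if the repeat test has come back within the limit. Such a participant is interrupted but never discontinued, and so falls outside the only incidence that 5.2.6 promises.

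The laboratory gap is related. The protocol describes the drug's laboratory effect, and acts on it, as a grade increase within a participant. By-visit summaries show how the distribution moved, not how many participants worsened by a grade at any time. The pilot increases were mostly Grade 1 and without bleeding, which are the ones an investigator is least likely to record as clinically significant. At stake is whether the report can show by arm how often treatment was interrupted and how many participants had a grade increase in coagulation or liver tests.

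**Working it through.** **1. Follow a participant who pauses and resumes.**

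| Place in SAP | Would this participant be counted as interrupted? |
|---|---|
| 3.4(d) endpoint | Yes, by definition |
| 5.2.6 analysis list | No, discontinuation only |
| 5.2.6 AE-related text | Listed if due to an AE; count and proportion for discontinuations only |
| 5.1.3 compliance | Missed doses lower the percentage, but no interruption is counted |
| Appendix A | Four removals: exploratory endpoints, other PSAs and placebo sharing, the interim analysis, events of special interest. Interruption is not among them |

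An interruption for a reason other than an AE is not even listed.

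**2. Follow a one-grade INR increase.** It contributes to the by-visit change in 5.2.8. It enters the AE tables only if judged clinically significant. C 12.1 asks for no extra follow-up after a one-grade increase, so many such increases may never become AEs. The out-of-range flag does not isolate worsening, because C 3.4.1.1 says INR or aPTT was often mildly abnormal at baseline.

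**3. Reproduce the pilot figures.** C 5.4 gives 20 to 21 patients per group, and C 3.1 gives 41 on upamostat in two groups, so one group had 20 and the other 21.

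- Placebo: 5/20 = 25%. 200 mg: 10/20 = 50%. 400 mg: 13/21 = 61.9%, the stated 62%.
- C 5.4 gives 65% for the 400 mg group. That is 13/20. With 21 patients it cannot arise (13/21 = 61.9%, 14/21 = 66.7%). The 400 mg AE rates in C 5.4 (19% and 10%, that is 4/21 and 2/21) point to 21 patients.
- Fisher's exact test on the reconstructed 5/20 against 13/21: two-sided p = 0.028. The exact 95% interval for 13/21 is 38% to 82%.

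**4. What a by-arm comparison could show.** The outcome is a rise of at least one grade in either INR or aPTT, as in the pilot. With n per arm, power is the sum over all (i, j) of Bin(i; n, 0.25) × Bin(j; n, p) for the pairs where Fisher's two-sided p is below 0.05. The 95% half-width for the difference is 1.96 × √[(0.25 × 0.75 + p(1 − p))/n].

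| n per arm (assumed) | Power, p = 0.62 | Power, p = 0.50 | Half-width, p = 0.62 |
|---|---|---|---|
| 40 | 0.900 | 0.559 | ±20 points |
| 60 | 0.982 | 0.760 | ±16 points |
| 75 | 0.996 | 0.863 | ±15 points |

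Example at n = 75: 1.96 × √[(0.1875 + 0.2356)/75] = 0.147.

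The arm sizes are assumptions. SAP Appendix A says enrolment ended before the interim trigger, which protocol C 13.6 sets at 150 participants reaching Day 28. The documents do not give the achieved number.

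**The case against.** The strongest reply is that little is lost. INR and aPTT are summarised by arm and visit, and SAP 4.8 gives these summaries quartiles and extremes, so a shift between arms would be visible. Clinically significant abnormalities are graded and tabulated by arm. The protocol's own safety analysis section plans no graded laboratory table, so its absence is a gap in both documents and not a departure by the SAP. Interruption remains an SAP endpoint, AE-related interruptions are listed, and the listing sentence follows the protocol. A coagulation pause needs a rise of more than 2 grades, so on the pilot's evidence few would be expected.

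Most of this stands, and it rules out several stronger readings:

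- A reader might infer that the trial could not detect the coagulation effect at all. It could, as changes in value; what is missing is the comparison by grade.
- A reader might infer that the table would test whether the effect is dose-related. With one active dose, no analysis of this trial can.
- A reader might infer a known graded liver effect. The COVID-19 pilot saw no transaminase increase over placebo, and C 3.4.1.1 reports only transient increases, without grades, from randomised trials.
- A reader might infer that the SAP abandoned the interruption endpoint. It did not; it left out part of the summary.

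The reply does not close the gap in 5.2.6. A listing or a compliance percentage is not an incidence by arm, and expecting few events is no reason to leave a named endpoint uncounted.

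**Conclusion.** The point holds in two limited parts. First, SAP 3.4(d) and 5.2.6 disagree, and no recorded change explains it. As written, participants who pause and resume are counted as interruptions in no by-arm summary. This follows from the text and needs no assumption.

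Second, grade increases in INR, aPTT and the liver tests are not tabulated by arm unless they become AEs, so the pilot's mostly Grade 1 coagulation effect would largely go uncompared on the protocol's scale. How much is missed depends on how often investigators call a Grade 1 change clinically significant, which the documents do not say.

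The power figures are indicative only. They apply to the INR-or-aPTT composite and not to single analytes. They rest on assumed arm sizes and on pilot rates from about 20 patients per group, graded by CTCAE where this trial uses DAIDS. The range 0.56 to 0.996 shows how much depends on those inputs. Safety tests are optional in 5.2.6, so the case rests on describing the effect and its interval, not on a significance test.

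**What to change.** - **SAP 5.2.6:** report by arm the count and proportion with all-cause IP discontinuation or interruption, and with interruption separately, by reason. A pooled figure alone would not show how often the pause rules interrupted treatment.
- **SAP 5.2.8:** add, by arm, the number and proportion whose worst post-baseline DAIDS grade increase is at least 1, at least 2 and more than 2. Do this for either INR or aPTT (the pilot's composite) and for INR, aPTT, ALT, AST and bilirubin individually. Give the difference and 95% interval as in SAP 4.8. The liver tests are included because of their pause rule.
- **SAP Appendix A:** record both changes and their timing relative to unblinding.
- **Protocol C 3.4.1.1 and C 5.4:** reconcile 62% with 65%. Label any power figure with its assumed arm size and the CTCAE source of the rates.

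The cost is one or two extra tables from laboratory and dosing data the trial should already hold. No clinical rule changes.

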C 5.3 Scientific Rationale for Study Design

The purpose of this PSA is to evaluate the safety and efficacy of upamostat for early outpatient COVID-19 treatment. The platform trial design will maximize efficiency within the trial to allow for sharing of controls. Interim analysis plans will allow for early stopping for success, futility or if there is a safety signal.

C 5.4 Justification for Dose

Doses of 200 and 400 mg upamostat daily were well tolerated in previous studies. In a healthy volunteer study in which patients were given 100, 200 or 400 mg upamostat or placebo daily for 14 days, no difference in tolerability was noted among the upamostat doses. Similarly, in a pancreatic cancer study in which all patients received standard therapy, gemcitabine, and were randomized to either no additional treatment, 200 or 400 mg upamostat daily, both dose levels of upamostat were well tolerated.

In a pilot study of upamostat for treatment of COVID-19, patients received placebo, 200 or 400 mg upamostat daily for 14 days. Both dose levels were well tolerated, with no increase in clinical adverse events over placebo. Clinical adverse event rates (Grade 1, Grade 2) were 10%, 20% in the placebo group, 25%, 0% in the upamostat 200 mg group and 19%, 10% in the

upamostat 400 mg group. The only laboratory effect noted was an increase in the incidence of Grade 1 increases in INR or aPTT in the upamostat-treated patients as compared to those receiving placebo, noted in 25% of placebo patients, 50% of upamostat 200 mg patients and 65% of upamostat 400 mg patients. Most of these were one grade increases and none was accompanied by any bleeding.

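### The SAP plans no by-arm count of INR/aPTT grade increases, the unit in which the pilot's laboratory effect was reported and the protocol's pause rules are written

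*SAP*

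**What the plan says.** SAP 5.2.8 plans three outputs that cover INR and aPTT.

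- By arm: "Observed and changes from baseline in laboratory values will be summarized by treatment group and scheduled visit".
- Through the adverse event (AE) tables: "Laboratory abnormalities considered clinically significant will be entered by the investigators as adverse events and graded". SAP 5.2.6 then applies: "All AE will be summarized by worst DAIDS grade", split by system organ class, preferred term and treatment group.
- By subject: "Laboratory values outside the corresponding normal ranges will be flagged in listings".

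The protocol gives the background. C.3.4.1.1 reports from the COVID-19 pilot that "25% of placebo patients, 50% of upamostat 200 mg recipients and 62% of upamostat 400 mg recipients developed increases in either INR or aPTT", counting any rise of one CTCAE v5.0 grade or more, and adds that almost all were Grade 1 and that no clinical bleeding was seen. It also says that INR or aPTT "were often mildly abnormal at baseline in patients in the COVID-19 study". C 5.4 states: "The only laboratory effect noted was an increase in the incidence of Grade 1 increases in INR or aPTT", and gives 65% rather than 62% at 400 mg.

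The protocol's safety rules count in grades above baseline, on the DAIDS scale. Under C 12.1 a rise in INR or PTT of more than 2 grades pauses treatment, and a 2-grade rise adds follow-up. In C 12.2, Table 1 has a PSA pause considered when verified rises of more than 2 grades occur in more than 2 patients.

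**The concern.** The sponsor already knows of one on-drug laboratory effect and measured it as the share of participants with a grade increase. The SAP summarizes the same parameters by arm on a different scale. A reader of the report would see how INR and aPTT moved at each visit. The reader would not see how many participants per arm rose by one grade, by two, or past the more-than-2-grade limit that pauses treatment.

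The AE route is unlikely to fill this gap. It depends on an investigator's judgement of clinical significance, and C 12.1 asks for no additional follow-up after a 1-grade rise, the size of most pilot increases. The at-stake item is the safety description of the 400 mg dose; efficacy is untouched.

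**Working it through.** **Step 1. Does any planned output give the count?**

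| Planned output | By arm? | Number of participants with a grade increase over baseline? |
|---|---|---|
| Observed values and changes, per scheduled visit (SAP 5.2.8) | Yes | No. Summary statistics for each visit. They do not combine a participant's visits or apply a grade threshold. |
| AE tables by worst DAIDS grade (SAP 5.2.6) | Yes | Only for abnormalities judged clinically significant and entered as AEs. |
| Listings flagged against normal range (SAP 5.2.8) | No | No. A flag marks a value outside the range. With baselines often mildly abnormal, it does not identify an increase. |
| Counts for categorical safety measures (SAP 5.2.6) | Yes | Not named. The example given is hospitalization. |
| Study drug discontinuations due to AEs (SAP 5.2.6) | Yes | No. Coagulation is not separated out. |

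No planned output supplies the count.

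**Step 2. Reproduce the pilot figures.** C 5.4 gives 20-21 patients per group. The only whole-number counts that fit are 5/20 = 25%, 10/20 = 50% and 13/21 = 61.9% (62%). The 65% in C 5.4 fits 13/20, so the two 400 mg figures could be the same 13 patients over different denominators. These counts are inferred, not stated.

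**Step 3. Precision of the pilot difference.** Half-width = 1.96 × sqrt[p1(1−p1)/n1 + p2(1−p2)/n2].

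- 13/21 v 5/20: difference 61.9 − 25.0 = 36.9 points.
- Half-width = 1.96 × sqrt(0.619 × 0.381/21 + 0.25 × 0.75/20) = 28.1 points.
- 95% CI about 8.8 to 65.0 points.

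**Step 4. Precision of the missing table.** The number analyzed is not in the documents. SAP Appendix A says only that enrollment ended before the interim trigger, which C 13.6 puts at 150 participants (75 on upamostat) reaching Day 28. That does not cap the number randomized. The sizes below are assumptions; 150 per arm is the planned maximum. The second scenario halves the gap: 25 + 37/2 = 43.5%.

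| Assumed n per arm | 62% v 25%: 37 points, half-width | 43.5% v 25%: 18.5 points, half-width |
|---|---|---|
| 40 | 20.2 | 20.4 |
| 60 | 16.5 | 16.7 |
| 75 | 14.7 | 14.9 |
| 150 | 10.4 | 10.5 |

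At every assumed size the interval is narrower than the pilot's. At the pilot rates it would exclude zero throughout (37 − 20.2 = 16.8 points at n = 40). At half the gap it would include zero at n = 40 (18.5 − 20.4 = −1.9) and exclude it at n = 60 (18.5 − 16.7 = 1.8).

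**The case against.** **The plan already covers much of this.** Changes from baseline by arm at Day 3 and Day 14 bear directly on a coagulation effect, and the listings keep each participant's values. Rises of more than 2 grades trigger a pause, a repeat test and prompt reporting under C 12, and C 13.5.1.3 has the DSMB review unblinded selected laboratory data monthly. No safety endpoint in either document promises a laboratory-grade incidence, and most of what would be counted is Grade 1. All of this stands and keeps the point small. It does not supply the count: pause rules and DSMB review protect participants during the trial but put no by-arm estimate in the report.

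**The pilot rates are not a direct benchmark.** The pilot graded by CTCAE v5.0 and this trial uses DAIDS. That stands, and it limits comparison with the pilot. It does not limit the comparison between arms here.

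**Other documents may fill the gap.** The Master Protocol and DSMB Charter were not available, so a laboratory grading table specified there cannot be ruled out.

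Two stronger readings are tempting and are not supported.

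- *The Day 14 summary is diluted by late draws.* A reader might infer this from the ±2 day visit window, since dosing ends on Day 13. But C 9.4.6 sets the draw at 22-26 hours after the previous dose, nothing shows how many draws were late, and the window is the same in both arms. The table proposed here would not change draw timing either.
- *The AE tables are shown to miss the effect.* A reader might infer this because the pilot saw "no increase in clinical adverse events over placebo" while coagulation grades rose. That statement concerns clinical AEs, which C 5.4 reports separately from the laboratory effect. This trial's AE tables also admit laboratory abnormalities judged clinically significant, so the pilot line does not show what they would capture.

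**Conclusion.** The point holds as a low-severity improvement. SAP 5.2.8 gives no by-arm estimate of INR/aPTT grade increases, which is how the protocol describes the known effect and how its pause rules are written.

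A reader might go further and infer that the report could not show whether the pilot effect recurred. The documents do not support that: the by-visit changes may show a shift. What would be missing is the proportion affected per arm, with its difference and interval.

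The pilot difference was about 37 points, with an interval of about 8.8 to 65.0. A by-arm count here would narrow the half-width from 28.1 points to roughly 20 at 40 per arm or 15 at 75. Those figures rest on assumed sample sizes, on inferred pilot counts, and on borrowing CTCAE rates for a DAIDS-graded trial. The finding itself needs none of them; it rests on what the SAP lists. The primary endpoint is not affected.

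**What to change.** Add one table to SAP 5.2.8, by treatment group.

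- **Measure:** number and proportion of participants whose worst post-baseline DAIDS grade for INR, for aPTT, and for either is ≥1, ≥2 and >2 grades above baseline.
- **Period:** first dose through the Day 14 visit.
- **Samples:** scheduled and unscheduled, whether or not entered as AEs.
- **Denominator:** Safety Population participants with a baseline and at least one post-baseline result in that period.
- **Comparison:** difference in proportions with its 95% CI, the convention SAP 4.8 sets for binary endpoints.

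Keep the by-visit summary as planned. Record the addition in SAP Appendix A, or in the CSR if it is made after unblinding.

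**Cost.** One descriptive table from data already collected, on the scale the SAP already uses for AEs. Grades have to be derived from the laboratory values and each laboratory's reference range. Unscheduled samples taken on clinical judgement give some participants extra chances to be counted. Repeats under the C 12.1 INR/PTT pause rule do not add to the count, because the value that triggers them is already more than 2 grades up.
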